Specific Aim 1a. To evaluate the feasibility and acceptability of a 9-month TRF intervention compared to a standard dietary weight loss intervention (i.e. RCD). Feasibility of enrollment and retention, and acceptability of the intervention will be assessed in adults with obesity meeting inclusion/exclusion criteria proposed for the future large-scale trial. We will assess adherence to the weight loss programs, as measured objectively with a novel smartphone application and verified with CGM data, and subjectively with the use of questionnaires. We expect adherence to the RCD+TRF intervention will be similar to the RCD group, suggesting acceptability for a future large-scale trial. If we find differences in adherence between programs, the data will be used to optimize the RCD+TRF program prior to the future large-scale trial.

Specific Aim 1b. To assess the efficacy of RCD+TRF compared to RCD alone in producing weight loss at 12 weeks and reducing the risk of weight regain after 6 months of follow-up. Although the number of subjects included in this pilot study does not provide sufficient statistical power to detect differences in weight loss between groups, the data obtained will provide estimates of variability and effect size to assist with power and sample size calculations for the future large-scale trial

Exploratory Aim. To explore potential mechanisms contributing to any observed differences between groups we will evaluate (A) objective measures of free-living behavior (energy intake, physical activity, and sedentary behavior) and (B) objective measures of glucose variability, sleep and energy metabolism Preliminary data on free-living behaviors and

in-laboratory measures of sleep and energy metabolism will allow us to further optimize a future trial and probe mechanisms to explain any weight loss differences between groups.

II. Background and Significance:

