- **Feasibility and tolerability of the interventions** assessed by enrollment and retention numbers, protocol related adverse events (AE's), and questionnaires assessing satisfaction, quality of life and mood.
- Adherence to interventions assessed both with self-report and with the use of a smartphone application in conjunction with continuous glucose monitoring.

Secondary Outcomes:

- Weight (scale) and body composition (DXA) obtained at baseline (prior to the weight loss intervention), at 12 weeks (following the weight loss intervention), and at a 6mo follow-up time point.
- Physical activity assessed by accelerometry
- Free-living sleep patterns assessed by wrist actigraphy
- Objective (in-laboratory) sleep recording using Compumedics Inc Siesta digital sleep recorders
- Meal timing and energy intake assessed by photographic food records
- Patterns in 24h glucose assessed by continuous glucose monitors over 7 days before and after the weight loss intervention
- Questionnaire based measures of appetite
- HqbA1c and lipids
- Resting metabolic rate and nocturnal energy metabolism by indirect calorimetery

B. Description of Population to be Enrolled:

Inclusion criteria.

- Adult males and females with a BMI of 27-45 kg/m² and weight stable over the previous 6 months;
- Age, 18-50 years old;
- Passing medical and physical screening, and analysis of blood and urine screening samples:
- Typical eating duration >12 hours per day (assessed by questionnaires);
- Own a smartphone
- Reside or work within approximately 30 minutes driving distance of CU-AMC (potential
 participants living outside of this driving distance could be included in the study at the PIs
 discretion).
- For participants in the optional Reproductive Hormone Sub-study: females, age 18-40, with regular menstrual cycles (between 18-40 days).

Exclusion criteria.

- Pregnancy or lactation for women (women who are >6 months postpartum with no plans of becoming pregnant in the next year and who are not currently lactating can be included; oral contraceptives will be allowed if medication has been consistent for the prior 6 months)
- Postmenopausal women (menopausal status will be assessed during the history and physical, with requirement of self-reported regular menstrual cycles for the last year; women who have undergone hysterectomy but with ovaries in place who continue to have regular menstrual symptoms can be included)

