El and meal timing will be measured using photographic food records by utilizing the camera function of participants' smartphones to take a picture of the food or beverage. Participants will be provided with detailed instructions regarding methods of taking food photographs, as outlined by the CTRC Nutrition Core. After taking the photographs, participants will text photographs directly to either a Meallogger account or a Google Voice account (note: an amendment was submitted in 1/2020 to switch to Google Voice after data collection using Meallogger in Cohorts 1 and 2 were already completed.). Subjects will be asked to record every intake event for 7 continuous days. The data from this 7-day recording period will be used to assess timing of energy intake in both groups, and adherence to time restriction in those patients in the RCD+TRF group. In addition, this information will be compared with data from continuous glucose monitoring to determine whether glucose excursions exist in the absence of recorded food intake events. Based on published data⁴⁰ showing that mean post-prandial glucose excursions in patients with normal glucose tolerance are ~40.5 mg/dL, this threshold will be used to indicate an episode of food intake. El will be estimated using the food images collected during the last 3 days of the 7 day recording period by staff in the CTRC Nutrition Core, as previously described^{41,42}.

Glucose variability: Free-living plasma glucose levels will be measured with a glucose monitoring

system (FreeStyle LibrePro, Chicago, IL) for 7 continuous days coinciding with the cell phone-based meal tracking described above. The device consists of a sensor applied to the back of the patient's upper arm that measures glucose in interstitial fluid every 15 minutes.

Patterns of PA and Sedentary Behavior: The activPAL3 micro (PALTechnologies, Glasgow, Scotland) will be used to estimate time spent in moderate-to-vigorous PA (MVPA), light activity, and sedentary behavior over a 7-day period at baseline. The activPAL3 micro uses accelerometer-derived information about thigh position to estimate time spent in different body positions. The time-stamped "event" data file from the activPAL software will be used to determine time spent sitting, standing, and stepping per day.

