Nocturnal energy metabolism: Participants will be invited to spend a night in the UCH whole room calorimeter for the measurement of nocturnal energy metabolism. We aim to perform approximately n=5 room calorimeter studies per group depending on budget. To facilitate recruitment for the optional procedure, the evening spent in the room calorimeter could be completed any night following study enrollment and prior to starting the weight loss intervention (except for during the 7-day free-living assessment of meal timing. El. and activity described above). Prior to the room calorimeter stay, participants will be asked to perform 3-days of sleep logs and cell phone based meal logging with time stamps to ensure meal and sleep timing are consistent prior to the chamber stay. Subjects will be provided an energy balance diet (calculated as RMR times an individually determined activity factor) on the day of the overnight chamber stay at baseline. The macronutrient composition of the diet will be the same at baseline and at the 12week follow-up: carbohydrate = 50%, fat = 35%, and protein = 15% (percent daily caloric intake:25% breakfast, 30% lunch, 35% dinner, and 10% afternoon snack). The meals will be eaten over a 12 hour period as follows: subjects will be asked, "when can you eat your first meal in the morning? (1, 2, or 3 hours after waking?)". This clock time will be T0. The meal times are then set at +5 (lunch), +8 (snack). +11.5 (dinner) after T0. . Subjects will arrive at the CTRC at least 2 hours before dinner and be placed in the room calorimeter at their habitual bedtime for measurement of nutrient oxidation and energy expenditure as previously described⁵⁵. Substrate oxidation will be calculated from urine nitrogen excretion, O2 consumption and RQ based on published equations⁵⁶. The chamber stay will be repeated at the 12-week follow up (between

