Dietary and Activity Prescriptions. Both groups will focus on caloric restriction to decrease overall EI. Participants will be given a personalized calorie goal based on their measured RMR. If RMR by indirect calorimetry and by Mifflin St-Jeor equation differ by >10%, then the average of the 2 values will be used. This estimated RMR will be reduced by 10% and then rounded to the nearest 100 kcal

Suggested macronutrient content (55% carbohydrates, 15% protein, 30% fat) will be the same for both groups. Participants in the RCD group will not be given any specific instruction regarding timing of food intake. Participants in the RCD+TRF group will be instructed to eat only during a window of 10 hours, starting within 3 hours of waking. They will also be instructed in specific strategies to support TRF including: strategies to deal with hunger outside eating windows, distraction techniques, and choosing a balanced diet/appropriate portions during feeding windows. All participants will be counseled on the importance of PA for weight loss and will receive a recommendation to perform 150 min/wk of PA.

Self-Reported Dietary Adherence, Effort, and Self-Efficacy: At weeks 4, 8 and 12, participants will be asked to rate on a 1-10 Likert scale: 1) how adherent they were to prescribed study diet over the past week, 2) how hard was it to adhere to prescribed study diet over the past week, and 3) how likely they feel they can adhere to prescribed diet for the next month³⁰. These questionnaires will also be administered monthly from month 4 through 9 to determine whether participants have continued to follow their prescribed dietary pattern. In addition, participants will be asked to use the Meal Logger app (Cohorts 1 and 2) or Google Voice at weeks 4 and 8, and monthly between months 4 and 9 in order to objectively assess adherence to the dietary intervention.

Intervention Safety and Tolerability: Participants will be asked to report AEs to study staff as they occur, to be reported to our IRB as per institutional guidelines. We will collect additional parameters to assess tolerability at week 12 and at the 6 month follow up visit. Quality of life (QOL) will be assessed with the RAND-36^{49,50} physical and mental health component summary score. Mood state will be assessed with the Profile of Mood States 2 (POMS-2)⁵¹⁻⁵³. Eating behaviors will be assessed with the Three Factor Eating Questionnaire (TFEQ)⁵⁴.

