Adherence: Adherence to the prescribed study diet will be objectively assessed through review of meal logs collected with the MealLogger app and Google Voice account as described above, as well as through evaluation of glucose excursions in comparison with the meal logs in order to determine if glucose excursions exist in absence of recorded food intake. In addition, adherence will be assessed subjectively as described above through the use of questionnaires using Likert scales to address ability to adhere to the study diet.

Post-intervention assessments. Within 3 weeks following the initial 12-week weight loss intervention all participants will complete 7 days of free-living EI recording (cell phone app), PA recording (accelerometers), sleep recording (wrist actigraph), appetite recording (VAS), and glucose monitoring (CGM) as described above for the baseline assessments. Participants will also have repeat assessments of HgbA1c, lipid panel, resting metabolic rate and body composition (DXA) during an outpatient CTRC visit. Participants will also repeat questionnaires as described above: adherence to the dietary intervention, QOL (RAND-36), mood state (POMS-2), eating behaviors (TFEQ), and sleep questionnaires (Berlin Questionnaire, Epworth Sleepiness Scale, Pittsburgh Sleep Quality Index, and Morningness -Eveningness Questionnaire). Participants completing the optional in-laboratory room calorimeter and objective sleep measurements at baseline will be asked to complete follow-up measurements. The follow-up measurements of sleep and nocturnal energy metabolism can be completed on any evening starting at week 10 of the intervention not to exceed 4 weeks following completion of the intervention. The only exception is that the inpatient visit cannot occur during the 7 days of free-living EI, PA, and glucose monitoring.

COVID-19 Post Intervention Changes

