Due to the COVID-19 pandemic, we are unable to carry out week 12 measures as described above. Instead, the study team will drop off the accelerometer and wrist actigraph to participant's homes. The packet of devices will be left on the participant's doorstep to eliminate person to person contact. Proper PPE will be worn by the study team during the drop-off and pick-up time including gloves and masks. The participants will be asked to wait a few days before wearing the devices and encouraged to wipe each device down before placing it back in the packet for pick-up. Once the participants have worn the device for 7 consecutive days, the study team will pick up the devices from the doorstep and wipe down the packet with a disinfecting wipe. The devices will not be handled by the study team for at least 1 week post pick-up. The devices will be handled as follows:

- The study team will wear gloves and a mask any time they are handling devices
- Devices will be disinfected with a Cavi-wipe before being placed in the individual device packets
- Each device will be placed in its own sanitized plastic bag before being placed in the device packet
- Devices will be given to the entire cohort on one date, so that there will be no sharing of devices between participants
- No study team member will handle devices if they are exhibiting symptoms of COVID-19 or have been exposed in the last 14 days.

These measures will be put into place so long as the orders from campus, local, state, or federal government are such that the study measures cannot be carried out as originally planned. The study team will resume normal visit procedures once it is safe and permitted to do so.

We will still collect all non-contact outcomes such as the appetite recording (VAS), and the 7 days of food logging via Google voice. In addition to these measures, for the cohort participating in the weight loss intervention during the COVID-19 pandemic only, we will administer a questionnaire specific to COVID-19 (changes in work, levels of motivation, ability to adhere to the diet, etc) as well as the Perceived Stress Scale, a validated psychological instrument for measuring the perception of stress. CTRC measures such as the DXA, blood panel, and resting metabolic rate will not be collected under these circumstances.

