E. Potential Scientific Problems:

Adherence to the TRF protocol: This will be the first study to our knowledge that will assess the feasibility of using TRF in the context of a reduced calorie diet for weight loss. We will objectively measure compliance to the protocol at baseline and 12 weeks using CGM and photographic time-stamped food logs but will otherwise not know whether subjects randomized to the TRF group were compliant to the protocol. To limit the extent of possible non-compliance to the TRF arm we decided on a shorter intervention for our first study. We are also using a high intensity behavioral support program that will meet weekly to discuss dealing with hunger/cravings or other challenges that might be associated with TRF. We will also ask participants to keep a log documenting daily feeding duration (first and last energy intake events) during all intervention weeks.

F. Data Analysis Plan:

Sample Size Justification:. We will aim to recruit 60 participants in two cohorts.. The sample size was determined for the primary outcome, change in body weight (kg) at 12 weeks. Assuming 20% attrition, we will be left with n=48, or n=24 subjects per group. To justify the sample size, we computed the detectable difference that we have 80% power for based on existing preliminary and published data. We will assume an alpha=0.05 and use two-sample t-tests. We assumed that the RCD group will have similar weight loss as has been shown previously with the standard Colorado Weigh curriculum, in which the mean \pm standard deviation (SD) weight loss using an intent-to-treat analysis at 12 weeks is -4.1 \pm 3.7kg⁵⁷. There are no prior relevant data for 12-week weight loss using TRF in the context of a weight loss intervention. However, prior data from the Gill and Panda study²⁶ of time restricted feeding without a weight loss intervention showed a mean weight loss at 16 weeks of -3.3 kg with a SD=3.4 kg. Given that we are combining the RCD and TRF treatments, the standard deviation is likely to be between 3.4kg and the sum of the variation of the RCD and

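### The CGM cutoff for an eating episode is a published mean rise with no detection rate, so a week without flags does not by itself verify adherence

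*Combined protocol and SAP*

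**What the plan says.** Section IV.C, Baseline Assessments (energy intake and meal timing), cites a published figure and adopts it as the cutoff for an eating episode: "mean post-prandial glucose excursions in patients with normal glucose tolerance are ~40.5 mg/dL, this threshold will be used to indicate" such an episode. The sensor reads every 15 minutes for 7 days, alongside photographic food logs. The Adherence paragraph of IV.C restates the purpose as a one-way comparison, to "determine if glucose excursions exist in absence of recorded food intake".

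Specific Aim 1a describes adherence "as measured objectively with a novel smartphone application and verified with CGM data". Section IV.A lists adherence, by self-report and by the app together with CGM, under Primary Outcomes, whereas the Statistical Analysis text in IV.F names change in weight as the primary outcome variable.

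Section IV.E limits the objective check of compliance to two points (before the intervention and at week 12) and admits the gap in these words: "using CGM and photographic time-stamped food logs but will otherwise not know whether subjects randomized to the TRF group were compliant". Under the COVID-19 changes, "the study team will drop off the accelerometer and wrist actigraph"; CGM is not listed among the measures kept for that period.

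The documents give no SD for the excursion, no detection or false-flag rate, and no reference glucose or time window that would define an excursion.

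**The concern.** A mean marks the centre of a distribution. Used as a minimum, it misses every meal whose rise is below average. Because the check looks only for rises without a logged intake, a cutoff that is too high errs in the reassuring direction: missed intake looks like adherence.

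This matters because the photographs, the Likert ratings and the daily log of first and last intake all come from the participant. CGM is the only adherence measure that does not depend on what the participant reports. Aim 1a uses adherence to judge whether the time-restricted program is acceptable for the larger trial and whether it needs changing. If quiet CGM weeks were read as confirmation, occasional unlogged eating outside the window could go unnoticed in that judgement.

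**Working it through.** **Inputs.** From the documents: cutoff c = 40.5 mg/dL, equal to the cited mean (IV.C). The figure comes from a cited study and has no inputs in the documents, so there is nothing to reproduce. Assumed, because no spread is given: symmetric, or lognormal with CV 0.3, 0.5 or 0.7.

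**Step 1: share of ordinary meals below the cutoff if the cited mean applies.** For a symmetric distribution, P(X < mean) = 0.50 whatever the SD. For a lognormal with mean μ, σ = √ln(1 + CV²) and P(X < c) = Φ[(ln(c/μ) + σ²/2)/σ]. With μ = c this reduces to Φ(σ/2):

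- CV 0.3: σ = 0.294, Φ(0.147) = 0.558
- CV 0.5: σ = 0.472, Φ(0.236) = 0.593
- CV 0.7: σ = 0.631, Φ(0.316) = 0.624

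**Step 2: if the trial's own mean differs.** The cited mean is for normal glucose tolerance. The trial enrols BMI 27-45 kg/m² and excludes a history of diabetes. Screening includes HbA1c and a metabolic panel, with abnormal chemistry left partly to the study physician's judgement, but no numeric glucose or HbA1c limit is stated. The mean could therefore be higher than cited. Reduced-calorie meals or small intakes could make it lower. The same lognormal formula with c = 40.5 gives:

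| Assumed mean (mg/dL) | CV 0.3 | CV 0.5 | CV 0.7 |
|---|---|---|---|
| 30 | 88% | 81% | 79% |
| 40.5 | 56% | 59% | 62% |
| 50 | 28% | 42% | 49% |
| 60 | 12% | 28% | 38% |

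**Step 3: what a week without flags shows.** With miss probability q per unlogged meal and independent meals, P(no flag after k meals) = q^k. The clustered row uses a beta-binomial with an assumed within-person correlation of 0.3.

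| Miss rate | k = 1 | k = 3 | k = 5 | k = 7 |
|---|---|---|---|---|
| q = 0.5, independent | 50% | 13% | 3% | 0.8% |
| q = 0.5, clustered | 50% | 24% | 15% | 11% |
| q = 0.8, independent | 80% | 51% | 33% | 21% |

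The q = 0.8 row corresponds to a mean near 30 mg/dL in Step 2. At q = 0.5, one unlogged meal in the week is as likely to pass unseen as to be flagged, while daily unlogged meals would probably raise at least one flag.

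**The case against.** The strongest reply is that the operative text is modest. It asks only whether rises occur without a logged intake, and a high cutoff is defensible for that question because it limits false accusations of non-logging. Nothing says that a quiet week will be reported as proof of adherence. This stands. The criticism attaches to the Aim 1a wording and to the missing detection rate, not to looking for unlogged rises.

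Second, the half figure depends on a source that the documents do not describe: which meals it averaged, how it defined an excursion, and with what spread. This also stands. A reader might infer that half of this trial's meals will be missed; the documents do not support that, and Step 2 shows that the share could be well below or well above half.

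Third, a reader might go further and infer that nearly all snacks would be missed. Smaller intakes are more likely to fall below the cutoff, but the only menu with meal sizes is a provided diet for an optional overnight calorimeter stay (about 5 participants per group), and the documents do not say how the rise scales with energy. No percentage for snacks can be defended.

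Fourth, limited CGM coverage might look like a concealed weakness. It is not: IV.E discloses it. What IV.E does not say is that the CGM check may itself miss intake during the weeks when it is worn.

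**Conclusion.** The point holds in a limited form. The cutoff equals a cited mean and has no detection rate. If that mean applies, about half of ordinary meals, or somewhat more, fall below it. Over assumed means of 30 to 60 mg/dL and CVs of 0.3 to 0.7 the missed share runs from 88% down to 12%, so the actual rate is unknown. An unknown rate cannot support a claim of verification for occasional or small unlogged intake, although flags remain useful and frequent non-logging of ordinary meals would probably be caught.

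A reader might infer that the comparison of arms is biased or that the trial's main analysis is affected. Neither is shown: the same cutoff applies to both arms, no differential miss rate can be derived from the documents, and no test, sample size or decision rule uses it. Severity is minor to moderate.

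**What to change.** 1. Keep 40.5 mg/dL as the pre-stated cutoff, and define the excursion by its reference glucose and time window.
2. From the baseline-week CGM and logged intake events, with the analyst blind to arm, report the share of logged events that reach the cutoff and the rate of excursions away from any logged event. The latter is an upper bound on false alarms, since some may be unlogged intake. Repeat at one or more lower cutoffs as a sensitivity analysis, fixed before the week-12 adherence comparison where still possible and otherwise labelled post hoc. The documents give no basis for a particular lower value, and Meallogger data collection in Cohorts 1 and 2 was already complete by the 1/2020 amendment.
3. Report the week-12 check beside these rates, identically in both arms, with the number of participants lacking CGM. Note that detection of logged events may overstate detection of smaller unlogged ones.
4. Replace the Aim 1a wording on verification with: *CGM in the week-12 assessment can detect some unlogged intake; an absence of flags does not confirm adherence.*

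The cost is a modest re-analysis of data that the plan already collects. Lower cutoffs will give more false alarms, which are reported beside them. Precision is adequate for a pilot. With 21 logged events each (3 per day, assumed) and within-person correlation ICC of 0.1-0.3 (assumed), the 95% half-width for a share near 50% is 1.96 × √[0.25 × (1 + 20 × ICC)/(21N)]. That is 4.8 points at N = 60 with ICC 0.1, and 8.2 points at N = 48 with ICC 0.3.

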Statistical Analysis: Efficacy Testing: Baseline demographic characteristics will be summarized by treatment groups using descriptive statistics. Any imbalance between groups will be examined using two-sample t-tests and Fisher's exact tests as appropriate. The primary analysis will use the ITT principle to test our study hypotheses under practical and realistic conditions when not all participants follow or complete the program. All randomized participants will be analyzed. A linear mixed effect model (LMM) will serve as the primary method to handle missing values. The normality assumptions will be evaluated and transformations used (e.g. square root and log) as appropriate. Change in weight is the primary outcome variable and others will be secondary outcomes. Consequently, no adjustment for multiple outcomes will be applied. P-values <0.05 will be considered significant. No interim analysis is planned. Any imbalance in baseline characteristics between groups that could potentially be a confounding factor for the outcome will be adjusted for in the statistical model (i.e., age, sex, level of PA achieved during intervention). Differences between groups in weight, fat mass, lean mass, MVPA, EI, sleep outcomes, and glucose variability will be compared using a LMM. Specifically, the test of time by group interaction will be used to assess efficacy. Pearson's correlations will be used to assess the relationship between sleep and nocturnal metabolism outcomes and longitudinal weight regain at 6 months. Variability of Major

Outcome Measures: Standard deviation and effect sizes will be determined based on the LMM model estimates to assist with planning the large-scale trial.

G. Summarize Knowledge to be Gained:

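### The plan does not provide for masking the staff who estimate energy intake from time-stamped food photographs, so the week-12 comparison between arms is open to assessor bias

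*Combined protocol and SAP*

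**What the plan says.** All references are to the combined protocol and SAP.

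- **How EI is obtained (IV.C, Baseline Assessments).** Participants photograph what they eat and drink for seven days and text the images to a study account. EI is "estimated using the food images collected during the last 3 days of the 7 day recording period by staff in the CTRC Nutrition Core", by a method for which two published sources are cited.
- **Other uses of the same record (same section).** The seven-day log also serves to "assess timing of energy intake in both groups, and adherence to time restriction in those patients in the RCD+TRF group".
- **Time stamps (IV.E).** Compliance is measured "at baseline and 12 weeks using CGM and photographic time-stamped food logs".
- **Repeat measurement (IV.C, Post-intervention assessments).** EI recording is repeated after the 12-week program by the baseline method. The COVID-19 changes keep the seven days of food logging.
- **What separates the arms (IV.C, Dietary and Activity Prescriptions).** RCD+TRF participants are "instructed to eat only during a window of 10 hours, starting within 3 hours of waking". For the other arm, "Participants in the RCD group will not be given any specific instruction regarding timing of food intake". Entry requires a habitual eating duration above 12 hours (IV.B).
- **Use of EI.** It is a secondary outcome (IV.A). The exploratory aim lists it among objective measures of behavior (Section I). In IV.F, "Differences between groups in weight, fat mass, lean mass, MVPA, EI, sleep outcomes, and glucose variability will be compared using a LMM", with efficacy judged by the group-by-time interaction.
- **Masking.** No section mentions masking or blinding of image readers or of any other assessor.

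**The concern.** Participants and class leaders in a diet trial of this kind cannot be blinded, but the person who turns a photograph into calories can be. Estimating portion size from an image involves judgement, and a reader who can guess the arm may judge differently without meaning to.

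Here the guess could come from the record itself. After randomization one arm is asked to eat within 10 hours and the other has no timing instruction, so the spread of image times over the day carries information about the arm. Clock time is needed for meal timing and window adherence. It is not needed for the calorie estimate.

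An arm-dependent reading error is systematic, so a larger sample does not shrink it. It could create, hide or enlarge an EI difference. That difference would then be offered as a mechanism for any weight result, and its effect size could carry into the planning of the larger trial.

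**Working it through.** The documents give no SD, effect size or power for EI, so there is no figure to reproduce. The check is a reading of the text, followed by an illustration on stated assumptions.

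**1. When can the times suggest the arm?** IV.C places the program after the baseline assessments and describes randomization at that point. Baseline images are therefore taken before the arms differ, and their times carry no arm signal. At week 12 the arms differ by instruction, so only the week-12 reading is exposed.

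**2. What reaches the test?** Let s be the mean reading error in an arm at a visit. The interaction estimates

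true effect + (s[TRF, wk 12] − s[RCD, wk 12]) − (s[TRF, base] − s[RCD, base]).

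By step 1 the last bracket is zero in expectation, as far as the image times are concerned. An error that depends on visit alone is equal in both arms and cancels. What remains is the week-12 difference between arms.

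**3. A suggestion is weaker than a label.** Suppose a reader shifts the estimate by b whenever the times look restricted. Let pT and pR be the proportions of image sets that look restricted in RCD+TRF and RCD. The bias is b × (pT − pR). It equals b only if times identify the arm perfectly, and it falls as RCD participants happen to eat within 10 hours or RCD+TRF participants do not adhere. The documents give none of b, pT and pR.

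**4. Size, by assumption only.** If intake were near 1,500 kcal/day and the net arm-dependent shift 5% to 10%:

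- 1,500 × 0.05 = 75 kcal/day
- 1,500 × 0.10 = 150 kcal/day

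The effect on the test depends on the SD of the quantity compared, also assumed. IV.F expects 24 per arm after 20% attrition. With a two-sided 0.05 t-test standing in for the mixed model, SE = SD × √(2/24). For SD 500, SE = 144.3, and a net error of 100 gives a noncentrality of 100/144.3 = 0.693 on 46 degrees of freedom. False-positive rates with no true difference (nominal 5%):

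| Net differential error (kcal/day) | SD 300 | SD 500 | SD 700 |
|---|---|---|---|
| 50 | 8.7% | 6.3% | 5.7% |
| 100 | 20.4% | 10.4% | 7.7% |
| 200 | 61.8% | 27.4% | 16.3% |

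The range runs from negligible to serious, and the documents do not say where this trial lies.

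**5. Size of the masking task.** EI uses three days per assessment: 60 participants × 2 assessments × 3 days = 360 photo-days at most. With 48 retained at week 12, (60 + 48) × 3 = 324.

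**The case against.** The strongest reply is that silence is not evidence of unmasked reading. The plan does not say what the readers are shown or whether they know the allocation, and the cited method sources cannot be checked here. The mention of "photographic time-stamped food logs" in IV.E concerns compliance, not the calorie estimate. Classes are led by a dietitian at a different center, and nothing says that the Nutrition Core delivers the intervention. This stands. A reader might infer that the staff see the times and know the arm, but the documents support only that masking is not provided for.

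A second tempting inference is that readers would expect RCD+TRF to eat less, so that the bias favors that arm. The protocol states no such expectation. Both arms have the same calorie rule and macronutrient targets, similar adherence is expected (Section I), and the background stresses benefits seen at similar or equivalent intake (Section II). The direction is unknown.

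The reply is also right that masked reading is not free and is incomplete. It adds a handling step, image content may still hint at the arm, and unblinded participants still choose what to photograph. The comparison of logs with CGM addresses unrecorded intake, but not how a recorded portion is judged.

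Finally, this is a pilot that says it lacks power even for weight, and EI is one of many secondary outcomes. That limits the weight of the point without answering it: the effect sizes are meant to inform a larger trial, and coding images is inexpensive.

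**Conclusion.** The concern holds in limited form. A plan followed as written leaves a judged outcome, compared between arms, without any provision for masking its assessors. At week 12 the record contains information that can suggest the arm.

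The exposure is confined to the EI comparison. Retention, adverse events, questionnaires, scale weight and adherence to the eating window do not use the calorie estimate. A reader might take 75 to 150 kcal/day, or the table of error rates, as an estimate of the bias in this trial. Neither is, because the intake level, the reader shift and the SD are all assumed.

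The conclusion itself rests on two points: that the 12-week images are read by the baseline method, as IV.C indicates, and that no masking rule exists outside these documents. If the Nutrition Core already reads coded images without times, one sentence saying so closes the point. This is worth fixing, but it does not threaten the trial's main results.

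**What to change.** Add to IV.C, under both the baseline and the post-intervention assessments, wording such as:

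> EI will be estimated from images coded to hide participant identity, arm, visit and time. Baseline and week-12 image sets from both arms will be read in random order. Meal timing and adherence to the eating window will be taken separately from the message record.

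Someone other than the EI readers should do the coding and keep the key.

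**Cost.** A relabelling and shuffling step for at most about 360 photo-days, a separate extraction of meal times, and holding baseline images until the week-12 sets are in. No extra reader, visit or participant procedure is needed.

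**Cohorts already collected.** IV.C notes that collection by the first app was complete in Cohorts 1 and 2 before the January 2020 change. Stored images not yet read can be coded in the same way. Any already read without masking should be reported as such. If masking proves impracticable, the plan should say so and describe EI as estimated by unmasked readers.

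**What remains.** Selective photographing by unblinded participants is untouched and should be stated as a limitation of the EI result.
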